13.1. Sub-study Design

This is a prospective/retrospective multicenter single arm sub-study within the main PAS cohort.

13.2. Sub-study Hypotheses

The safety hypotheses are:

- a) $H_0: P_{(\text{Freedom from device / system-related complications at 24 months})} \leq 80\%$
 $H_a: P_{(\text{Freedom from device / system-related complications at 24 months})} > 80\%$
- b) $H_0: P_{(\text{Freedom from pressure sensor failure at 24 months})} \leq 90\%$
 $H_a: P_{(\text{Freedom from pressure sensor failure at 24 months})} > 90\%$

The effectiveness hypothesis is:

$$H_0: Y_{(12 \text{ month heart failure [HF] Hospitalization Rate})} \geq Y_{(12 \text{ month HF Hospitalization Rate in CHAMPION trial Control group})} + \Delta$$

This confidential document is the property of Abbott and shall not be reproduced, distributed, disclosed or used without the express written consent of Abbott

Clinical Investigation Plan

$Ha: Y_{(12 \text{ month HF Hospitalization Rate})} < Y_{(12 \text{ month HF Hospitalization Rate in CHAMPION trial Control group})} + \Delta$

where Y (12 month HF Hospitalization Rate) = the HF hospitalization rate parameter at 1 year in the PAS, Y (12 month HF hospitalization rate in CHAMPION trial Control group) = the HF hospitalization rate in Part 1 of the premarket Control group, and Δ = non-inferiority (NI) margin of 0.10. The CHAMPION study Part 1 Control group had a HF hospitalization rate of 0.75 with a lower 95% confidence limit of 0.64. Therefore, a NI margin of 0.10 was chosen to account for the typical variability in HF hospitalization rates occurring between clinical trials. If the null hypothesis is rejected, it can be concluded that there was not a worsening in HF hospitalization rate in the PAS compared to the CHAMPION study Control group (i.e. non-inferiority is established).

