Sub-Study	The primary effectiveness objective is to demonstrate that there is

This confidential document is the property of Abbott and shall not be reproduced, distributed, disclosed or used without the express written consent of Abbott

Clinical Investigation Plan

Effectiveness Measures:	not a worsening in HF hospitalization rate at 1 year in the sub-study compared to the 1 year HF hospitalization rate in the CHAMPION study Control group (Part 1).
Sub-Study Statistical Considerations:	
Primary Safety Endpoints
 
The primary safety hypotheses are that the device / system-related complication-free proportion of subjects will be at least 80% at 24 months (OPC used in the CHAMPION trial) and that the pressure sensor failure-free proportion of subjects will be at least 90% at 24 months (OPC used in the CHAMPION trial). Plotting and analysis of safety endpoints will also be displayed using Kaplan-Meier methods.
 
All safety analyses will be performed on the safety population.
 
Primary Effectiveness Endpoint
 
The primary effectiveness evaluation will compare the HF hospitalization rate over 1 year in the sub-study to the 1 year HF hospitalization rate in the Control group (Part 1) of the CHAMPION trial.
 
The effectiveness population consists of all subjects who received a sensor implant regardless of study completion status.
 
Supplemental Analyses
 
To assess the effectiveness of the training program, the safety and effectiveness results will be reported for Academic Hospitals and Community Hospitals.
 
Effectiveness analyses will be performed by the following subgroups: Women, Men, Reduced Ejection Fraction (< 40%), Preserved Ejection Fraction (≥ 40%), Ischemic Etiology, Non-ischemic Etiology, With ICD/CRT-D, and Without ICD/CRT-D.

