13.4. Sub-study Sample Size

The Control group HF hospitalization rate for Part 1 of the CHAMPION study at 1 year was 0.75.

Using an exact one-sample, 2-sided Poisson 95% confidence interval with alpha of 0.05, 114 patients will provide 85% power to show a difference between the estimated Treatment rate of 0.52 and the Control rate of 0.75. Likewise, 130 patients are required to achieve 90% power to show a difference between the estimated Treatment rate of 0.52 and the Control rate of 0.75.

The 2 year attrition rate in CHAMPION was 49.1%, therefore 256 patients $(130/(100\%-49.1\%)) = 256$ is the minimum sample size for this analysis. However, the Independent Committee will identify all patients that are optimally managed and are clinically similar to the Control group in CHAMPION. Therefore, the eligible patients for this sub-cohort and the resultant sample size may be greater.

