13.5.4. Sub-study Effectiveness Endpoint

Heart failure (HF) hospitalization rate over 1 year in the PAS study compared to the 1 year HF hospitalization rate in Part 1 of the CHAMPION study Control cohort.

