13.9.2. Analysis of Sub-study Effectiveness Endpoints

The effectiveness evaluation will compare the annualized HF hospitalization rate at 1 year to the 1 year HF hospitalization rate in Part 1 of the CHAMPION trial Control patients. The estimate of the rate will be tested with a NI margin of 0.10 and presented with 95% Poisson confidence intervals.

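### The sub-study power in section 13.4 is for 0.52 against 0.75 with no margin, while the planned non-inferiority test is against 0.85; its own power is not stated and the no-worsening conclusion omits the margin

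*Combined protocol and SAP*

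**What the plan says.** **Hypothesis (13.2).** The null is that the sub-study rate is at or above the CHAMPION Part 1 Control rate plus Δ, with a "non-inferiority (NI) margin of 0.10. The CHAMPION study Part 1 Control group had a HF hospitalization rate of 0.75". On rejection, "it can be concluded that there was not a worsening in HF hospitalization rate in the PAS", with the Control group as comparator, and the sentence ends by equating this with non-inferiority.

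**Analysis (13.9.2).** "The estimate of the rate will be tested with a NI margin of 0.10", with 95% Poisson confidence intervals presented. No other test is named.

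**Sample size (13.4).** By an exact one-sample, two-sided 95% Poisson interval, "114 patients will provide 85% power to show a difference between the estimated Treatment rate of 0.52 and the Control rate of 0.75". For the same pair of rates, the section puts 90% power at 130 patients. Dividing 130 by one minus the 49.1% two-year attrition gives a minimum of 256. The committee may select more: "the eligible patients for this sub-cohort and the resultant sample size may be greater". The margin does not appear in this section.

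**Objective and endpoint.** The sub-study synopsis, under Effectiveness Measures, aims to show "not a worsening in HF hospitalization rate at 1 year in the sub-study compared to the 1 year HF hospitalization rate", the comparator being CHAMPION Part 1 Control. Section 13.5.4 defines the endpoint as "Heart failure (HF) hospitalization rate over 1 year in the PAS study compared to the 1 year HF hospitalization rate in Part 1", again with CHAMPION Control patients as comparator. Neither states the margin.

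**The concern.** A power statement should describe the test that will be run. Here the sample-size section and the analysis sections use different boundaries. A reader of 13.4 would take 90% as the chance that the sub-study meets its effectiveness criterion at a true rate of 0.52, and it is not. The power of the real test is stated nowhere, either at 0.52 or at rates closer to Control, where it matters more.

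The second matter is wording. Rejecting the null excludes a rate of 0.85 or more. It does not exclude rates between 0.75 and 0.85, which are worse than Control. Without the margin beside it, the no-worsening phrase promises more than the test delivers. This grows with sample size, because a larger cohort can pass with a higher observed rate.

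**Working it through.** **Inputs.** Control rate 0.75, assumed sub-study rate 0.52, sizes 114, 130 and 256, exact two-sided 95% Poisson interval (all 13.4); margin 0.10 (13.2, 13.9.2). The boundary of the planned test, 0.75 + 0.10 = 0.85, is derived and not printed in the plan.

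**Assumptions.** Control fixed at 0.75, one person-year (PY) per patient, no overdispersion. One-year attrition is not given, so person-years are shown as a range. 256 PY is full follow-up of the minimum sample. 130 PY applies the two-year attrition and gives dropouts no person-time, so it is an extreme lower end.

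**Formula.** With k events in PY person-years, the exact upper limit is chi2(0.975, 2(k+1)) / (2·PY). The test passes if this is below the boundary. Let c be the largest passing k. Power at true rate r is P(X ≤ c), with X Poisson of mean r·PY.

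**Step 1: reproduce the plan (boundary 0.75, true rate 0.52).**
- 114 PY: c = 67, mean 0.52 × 114 = 59.28, power 85.7%. Stated: 85%.
- 130 PY: c = 78, mean 0.52 × 130 = 67.6, power 90.5%. Stated: 90%.
- 130 / (1 − 0.491) = 255.4, rounded up to 256. Stated: 256.

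A normal approximation, n = [(1.96·√0.75 + z·√0.52) / (0.75 − 0.52)]², gives 113 and 130. The stated figures therefore belong to a comparison with 0.75 and no margin.

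**Step 2: the planned test (boundary 0.85, true rate 0.52).**
- 114 PY: c = 77, power 98.9%.
- 130 PY: c = 89, power 99.5%.
- 256 PY: c = 188, power above 99.9%.

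The sizes for 85% and 90% power fall to about 60 PY (59 to 62, because exact power is not smooth in n) and 70 PY.

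**Step 3: the planned test at other true rates.**

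| True rate | 130 PY | 256 PY |
|---|---|---|
| 0.60 | 90.2% | 99.7% |
| 0.75 (equal to Control) | 21.1% | 40.5% |
| 0.80 | 7.5% | 12.7% |
| 0.85 (null boundary) | 2.0% | 2.2% |

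The 0.85 row shows that, under these assumptions, the test holds its one-sided 2.5% level.

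**Step 4: largest observed rate that passes.** 89/130 = 0.685; 188/256 = 0.734. It first exceeds 0.75 at 333 PY (250/333 = 0.751), and does so for every size above 344 PY. At 400 PY it is 0.7575.

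**Step 5: overdispersion (assumption).** With a negative binomial count of variance 1.5 or 2 times its mean, power at 0.52 and 130 PY is 86.0% or 82.8% against 0.75, and 98.1% or 96.3% against 0.85. The mismatch stays conservative.

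**The case against.** The strongest reply is that nothing is harmed. The planned test is easier to meet than the one used for sizing, so 13.4 understates its power. Section 13.2 states the margin in the hypotheses and ties its conclusion to non-inferiority in the same sentence, and 13.9.2 repeats the margin. A synopsis and an endpoint definition may leave a margin to those sections. Passing at a true 0.75 or 0.80 is how any non-inferiority test behaves inside its margin. At the stated minimum of 256 with full follow-up, the largest passing observed rate, 0.734, is still below Control.

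Most of this stands, and it is why the point is minor. It does not remove the mismatch: 13.4 still gives the power of a test the plan does not run. Nor does it settle the wording, since the sample has no maximum and a cohort above 344 PY could report an observed rate above 0.75 under a no-worsening label.

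Three stronger readings are tempting and not supported:
- That the sub-study is underpowered. Step 2 shows the opposite at the assumed rate of 0.52.
- That the plan claims a rate below Control and lacks the test for it. The synopsis and 13.2 claim non-inferiority only, so the absence of a step against 0.75 is a design choice.
- That the general sub-study objective in the synopsis, to confirm safety and effectiveness relative to premarket, contradicts the hypothesis. It names no comparator rate or margin, so there is nothing to contradict.

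**Conclusion.** The sample-size statement is wrong as written, and the severity is minor. The 85% and 90% in 13.4 are not the power of the planned test, which at a true 0.52 is 98.9% (114 PY) and 99.5% (130 PY). The error is conservative and no patients need to be added. The no-worsening conclusion is supported only in the sense of excluding a rate 0.10 or more above the historical 0.75.

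The figures rest on a Control rate treated as fixed, although 13.2 gives it a lower 95% limit of 0.64. Carrying that error with a standard error of (0.75 − 0.64)/1.96 = 0.056 in a two-sample normal check still gives 97.4% (130 PY) and 99.6% (256 PY) power at 0.52 to meet the margin. The conclusion that the planned test is well powered at 0.52 therefore does not depend on that simplification.

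**What to change.** **1. Section 13.4.** State the boundary for each power figure: at 0.52 and 130 person-years, 90.5% against 0.75 and 99.5% against 0.85. Add the power of the 0.85 test at less favourable true rates, such as 0.60 (90.2% at 130 PY, 99.7% at 256 PY) and 0.75 (21.1% and 40.5%).

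**2. Sub-study synopsis, 13.2 and 13.5.4.** Add the 0.10 margin in the synopsis and 13.5.4. In the synopsis and 13.2, word the conclusion as: *not worse than the CHAMPION Control rate by 0.10 or more*.

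Both are text changes and need no patients, data or alpha.

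**Optional, only if the sponsor intends to say the rate is lower than Control.** Before the sub-study effectiveness analysis, pre-specify a second step taken only if non-inferiority is met: the upper limit of the same 95% interval lies below 0.75. The steps are nested, so no extra alpha is used. Word the result only as *lower than the historical Control rate*. Use an overdispersion-robust interval, and add a two-sample sensitivity comparison that carries the Control group's sampling error.

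This option has real costs:
- Its power at a true 0.60 is 53.0% (130 PY) or 81.1% (256 PY).
- If the true unguided rate were 0.64, a cohort with no benefit would pass 30.8% (130 PY), 52.6% (256 PY) or 66.9% (344 PY) of the time.
- With variance 1.5 or 2 times the mean, a plain Poisson interval would pass it about 5% or 8% of the time at a true 0.75.
- Version C is dated February 2018, after the enrollment completion planned for December 2017 in Appendix A, and 13.1 describes the design as partly retrospective. The amendment should state what data had been seen.

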13.3. Sub-study Population (device and control group)

These patients must be selected by an independent committee to be clinically similar to the CHAMPION study Control cohort and will be selected from the PAS Main Cohort.

The independent committee will identify optimally medicated adults from the main cohort with New York Heart Association (NYHA) Class III Heart Failure (HF) who have experienced a HF hospitalization within the past 12 months. This will be based on pre-enrollment information, and not on any information regarding what happened to the patient post-enrollment.

Efforts should be taken to have a fair representation of women (actual number not set as there may be unknown biases regarding optimal medication for women and men).

The Control patients from Part 1 of the CHAMPION study will set the performance goal.

13.4. Sub-study Sample Size

The Control group HF hospitalization rate for Part 1 of the CHAMPION study at 1 year was 0.75.

Using an exact one-sample, 2-sided Poisson 95% confidence interval with alpha of 0.05, 114 patients will provide 85% power to show a difference between the estimated Treatment rate of 0.52 and the Control rate of 0.75. Likewise, 130 patients are required to achieve 90% power to show a difference between the estimated Treatment rate of 0.52 and the Control rate of 0.75.

The 2 year attrition rate in CHAMPION was 49.1%, therefore 256 patients $(130/(100\%-49.1\%)) = 256$ is the minimum sample size for this analysis. However, the Independent Committee will identify all patients that are optimally managed and are clinically similar to the Control group in CHAMPION. Therefore, the eligible patients for this sub-cohort and the resultant sample size may be greater.

13.5. Sub-study Endpoints

13.5.1. Sub-study Safety Endpoints

Safety endpoints will be evaluated at 2 years:

- 1) Freedom from device/system related complications compared to OPC of 0.80
- 2) Freedom from pressure sensor failure compared to OPC of 0.90

13.5.2. Device / System-related Complication Criteria

A device / system-related complication is an adverse event that is, or is possibly, related to the system (wireless pressure sensor or external electronics) and has at least one of the following characteristics:

- is treated with invasive means (other than intramuscular medication or a right heart catheterization

This confidential document is the property of Abbott and shall not be reproduced, distributed, disclosed or used without the express written consent of Abbott

Clinical Investigation Plan

which is used for diagnostic purposes)

- results in the death of the subject
- results in the explant of the device

13.5.3. Sensor Failure Criteria

A Sensor failure occurs when no readings can be obtained from it after troubleshooting the system to rule out any problems with the external electronics.

13.5.4. Sub-study Effectiveness Endpoint

Heart failure (HF) hospitalization rate over 1 year in the PAS study compared to the 1 year HF hospitalization rate in Part 1 of the CHAMPION study Control cohort.

13.5.5. Sub-study Supplemental Analyses

Training Evaluation

To assess the effectiveness of the training program, the safety and effectiveness results will be reported for:

- 1) Academic Hospitals
- 2) Community Hospitals

Subgroup Analyses

The effectiveness analyses will be evaluated in each of the following subgroups:

- 1) Women
- 2) Men
- 3) Reduced Ejection Fraction (< 40%)
- 4) Preserved Ejection Fraction ($\geq 40\%$)
- 5) Ischemic Etiology
- 6) Non-ischemic Etiology
- 7) With ICD/CRT-D
- 8) Without ICD/CRT-D

13.6. Sub-study Enrollment Plan

These patients must be selected by an Independent Committee to be clinically similar to the CHAMPION study Control cohort and will be selected from the main cohort of the PAS.

13.7. Sub-study Length of Follow-up

The follow-up length for the PAS will be 24 months.

13.8. Sub-study Frequency of Follow-up Assessments

This confidential document is the property of Abbott and shall not be reproduced, distributed, disclosed or used without the express written consent of Abbott

Clinical Investigation Plan

Follow-up assessments will be made at Month 1, Month 6, and every 6 months thereafter for 2 years. Follow-up visits will include a physical exam, evaluation of NYHA Class, AE assessment, heart failure medications review, and assessment of any hospitalizations that may have occurred between visits.

13.9. Sub-study Statistical Plan

13.9.1. Analysis of Sub-study Safety Endpoints

The safety analyses will be based on the following objective performance criteria:

- a) the lower limit of the two-sided 95% confidence interval on the freedom from device / system-related complication rate at 24 months is at least 80%, and
- b) the lower limit of the two-sided 95% confidence interval on the freedom from pressure sensor failure rate at 24 months is at least 90%.

These safety endpoints will be tested hierarchically in order to control for multiplicity. First, the freedom from device / system-related complication rate will be tested. If the result is statistically significant (i.e., $p < 0.05$), then the freedom from pressure sensor failure rate will also be tested for significance (i.e., $p < 0.05$). The study will be judged to have provided positive safety results if both tests of the safety analysis endpoints are statistically significant (i.e., $p < 0.05$).

13.9.2. Analysis of Sub-study Effectiveness Endpoints

The effectiveness evaluation will compare the annualized HF hospitalization rate at 1 year to the 1 year HF hospitalization rate in Part 1 of the CHAMPION trial Control patients. The estimate of the rate will be tested with a NI margin of 0.10 and presented with 95% Poisson confidence intervals.

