11.6.2. Anticipated ADEs/SADEs

The following is a list of possible anticipated ADEs/SADEs:

- Hemoptysis
- Sensor not deploying
- Transient ischemic attack
- Atypical chest pain
- Sepsis leading to death
- Atrial arrhythmia leading to death
- Arterial embolism (upper extremity)
- PA (in-situ) thrombus
- Catheter site bleeding
- Catheter site ecchymosis
- Catheter site hematoma
- Vessel puncture site pain
- Cardiac monitoring abnormal
- Heart rate irregular
- Serum creatinine increased
- Dyspnea
- Congestive HF
- Ventricular tachycardia
- Dizziness
- Vessel perforation
- Sensor failure/malfunction
- Sensor migration

This confidential document is the property of Abbott and shall not be reproduced, distributed, disclosed or used without the express written consent of Abbott

Clinical Investigation Plan

- System not transmitting

Refer to the CardioMEMS™ PA Sensor and Delivery Catheter, Model CM2000 User Manual for more information. If it is not certain that an event meets the above definitions, contact the Project Manager.

For unexpected failure modes or unexpected adverse events, the site should follow their standard reporting practices for medical device reporting (MDR). As defined in 21 CFR 803, a MDR reportable event (or reportable event) means: An event that device user facilities become aware of that reasonably suggests that a device has or may have caused or contributed to a death or serious injury. A device user facility must report to sponsor and the FDA (no later than 10 days after awareness date) deaths and serious injuries that a device has or may have caused or contributed to, establish and maintain adverse event files, and submit summary annual reports to FDA.

STATISTICAL ANALYSIS

The data will be summarized using univariate statistics (e.g., N, mean, standard deviation, median, minimum and maximum) or frequency (e.g., N, %) as appropriate.

The primary time point for safety analyses is 24 months post enrollment. Enrollment is defined as having a successful Sensor implant. The primary time point for effectiveness analyses is 12 months post enrollment.

Unless otherwise specified, all statistical tests will be 2-sided with a significance level of 0.05.

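### The sub-study's non-inferiority test names only Poisson intervals for a repeat-event rate; under more than slight overdispersion the implied rule declares non-inferiority too often

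*Combined protocol and SAP*

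**What the plan says.** Section 13.9.2 gives the test in one sentence: the estimated rate is to be tested with a margin of 0.10 and "presented with 95% Poisson confidence intervals". It does not write out a success rule. The rest has to be put together from other sections:

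- **Boundary.** Section 13.2 sets the null as a rate at or above the CHAMPION Part 1 Control rate plus 0.10. Section 13.4 gives that rate: "The Control group HF hospitalization rate for Part 1 of the CHAMPION study at 1 year was 0.75". The boundary is therefore 0.85. Section 13.3 treats the control rate as a performance goal.
- **Method.** Section 13.4 sizes the sub-study "Using an exact one-sample, 2-sided Poisson 95% confidence interval with alpha of 0.05". It compares "the estimated Treatment rate of 0.52 and the Control rate of 0.75" and arrives at 114 patients for 85% power, then says that "130 patients are required to achieve 90% power". Dividing by one minus 49.1% attrition gives 256.
- **Parallel rule.** Section 12.7.1 decides the main-cohort effectiveness endpoint by the upper limit of a two-sided Poisson interval.
- **Level.** The opening of the Statistical Analysis section says that, unless otherwise specified, "all statistical tests will be 2-sided with a significance level of 0.05". That is 0.025 in the non-inferiority direction.
- **Endpoint.** Appendix L tabulates HF hospitalizations as events per patient-year, so one patient can contribute several events.

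No section mentions a robust variance, a negative binomial or quasi-Poisson model, a dispersion check, or a sensitivity analysis for clustering of events within patients. Mixed models appear only for quality of life, in 12.7.2.

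**The concern.** A Poisson interval sets the variance of the event count equal to its mean. With repeat admissions there are two ordinary reasons for the variance to be larger. One admission may make the next more likely in the same patient. Or the patients' underlying rates may behave like random draws from a spread of risks. In either case the count varies more than the interval allows, and its upper limit sits too low.

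That limit is what appears to decide the sub-study effectiveness question. Section 13.2 says that rejecting the null establishes non-inferiority, and section 14 sends effectiveness results to the FDA and into the device labeling. A limit that is too low lets a rate at the margin pass more often than the stated 2.5%. The 85% and 90% powers in 13.4 also rest on zero overdispersion.

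**Working it through.** **1. Reproduce the plan's sizes.** Inputs from 13.4: rates 0.52 and 0.75, exact two-sided 95% Poisson interval, one patient-year per patient. With x events in T patient-years the upper limit is chi2(0.975; 2(x+1)) / (2T). Take the largest x whose limit is below 0.75; power is P(Poisson(0.52T) ≤ x).

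- T = 114: x = 67, power 85.7%.
- T = 130: x = 78, power 90.5%.
- Score formula, (1.96√0.75 + z√0.52)² / 0.23²: 113.0 for 85% and 129.9 for 90%.
- Attrition: 130 / 0.509 = 255.4, rounded up to 256.

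The stated figures hold under pure Poisson counts.

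**2. Apply the same rule at the non-inferiority boundary.** With an upper limit required below 0.85, the sub-study passes with at most 89 events in 130 patient-years (limit 0.842) or 188 in 256 (limit 0.847). At a true rate of 0.85 under Poisson counts, the chance of passing is 2.0% and 2.2%. The exact interval is slightly conservative.

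**3. Add overdispersion.** The documents give no dispersion, so the variance/mean ratio V is an assumption shown over a range. Per-patient counts are negative binomial with mean μ and variance Vμ. The total over n patient-years is then negative binomial with size nμ/(V−1) and probability 1/V. For n = 256, μ = 0.85 and V = 2.0, the size is 217.6 and the probability 0.5; P(total ≤ 188) = 7.8%.

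| V (assumed) | Error at 0.85, 256 patient-years | Error at 0.85, 130 patient-years | Power, 0.52 vs 0.75, n = 130 |
|---|---|---|---|
| 1.0 | 2.2% | 2.0% | 90.5% |
| 1.25 | 3.6% | 3.3% | 88.0% |
| 1.5 | 5.0% | 4.7% | 86.0% |
| 2.0 | 7.8% | 7.3% | 82.8% |
| 2.5 | 10.3% | 9.8% | 80.4% |

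The error crosses 2.5% at V of about 1.05 with 256 patient-years and 1.10 with 130. If 256 are selected and the assumed 49.1% attrition holds, first-year exposure lies between these two: 256 × 0.509 = 130 if all losses came at the start, 256 if none came within the year.

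**4. Power against the boundary actually tested.** At a true rate of 0.52 and n = 130, the Poisson rule against 0.85 has power 99.5% at V = 1.0, about 96% at 2.0 and about 95% at 2.5. With 256 it is above 99.7% throughout.

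**5. Does the repair work?** A log-scale interval using the between-patient standard deviation s, m·exp(1.96·s/(m√n)) with m the mean count, was simulated 20,000 times per setting. Here k is the dispersion in variance = μ + kμ², so V = 1 + kμ.

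| k (assumed) | V at 0.85 | Poisson-rule error, 130 / 256 | Robust error, 130 / 256 | Robust power at 0.52 vs 0.85, 130 / 256 |
|---|---|---|---|---|
| 0 | 1.00 | 2.0% / 2.2% | 2.4% / 2.2% | 99% / >99.9% |
| 0.5 | 1.43 | 4.2% / 4.6% | 2.6% / 2.4% | 97% / >99.9% |
| 1 | 1.85 | 6.5% / 7.0% | 2.7% / 3.0% | 94% / 99.9% |
| 2 | 2.70 | 10.7% / 11.2% | 3.2% / 3.2% | 85% / 98.9% |

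The robust interval removes most of the excess error, but it is not exact.

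**The case against.** Several replies have force.

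- **The success rule is not written.** Section 13.9.2 attaches Poisson to how the interval is presented. This is correct: a limit below 0.85 is an inference from 12.7.1, 13.2 and 13.4. No other test or variance is named, so it is the natural reading, and the gap is itself a reason to state the rule.
- **A varied population is not enough.** A reader might infer that mixing ejection-fraction, etiology and device strata breaks the interval by itself. It does not: a sum of independent Poisson counts with different fixed rates is still Poisson. The argument needs clustering of events or rates treated as random draws. Selection of clinically similar patients (13.3) may also reduce the spread.
- **Any variation at all.** A reader might infer that the slightest overdispersion breaks the nominal level. The conservatism of the exact limit absorbs ratios up to about 1.05 or 1.10.
- **The size is assumed.** This is correct. The control rate of 0.75 with lower limit 0.64 (13.2) does not settle it: a Poisson interval gives 0.64 with about 220 to 240 control patient-years, while an assumed 275 would imply a ratio of about 1.15 to 1.35 and an error of about 3% to 4%. Control patient-years are not stated.
- **Power is ample.** For the 0.85 test, this is largely right. The fall from 90% to 80% belongs to the comparison with 0.75 and does not show that the non-inferiority test is underpowered.
- **It is late to change.** Version C is dated February 2018, after the December 2017 enrollment end anticipated in Appendix A; the study is open-label and rates are reported periodically. The change therefore needs documenting. It does not defeat the fix: the robust interval uses counts the study already collects and is generally wider when overdispersion is present, so the change makes success harder in the case that matters.

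**Conclusion.** The point holds as a gap in the analysis method. The plan names only Poisson intervals for a rate of repeat events and makes no allowance for overdispersion. Under the implied rule, the one-sided error at 0.85 rises from about 2% to between 3.3% and 10.3% over assumed variance/mean ratios of 1.25 to 2.5 and exposures of 130 to 256 patient-years.

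This rests on three assumptions: that the rule is an upper Poisson limit below 0.85, that overdispersion is of gamma-mixed (negative binomial) form, and that its size lies in the range shown. The documents fix none of the three, so the upper figures illustrate what could happen and do not predict what will.

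A reader might also infer that this one limit decides the whole sub-study. It does not: 13.2 and 13.9.1 set two safety hypotheses with their own criterion. The issue is control of false non-inferiority on effectiveness, not feasibility.

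**What to change.** In 13.9.2, write the success rule: non-inferiority is concluded if the upper limit of the two-sided 95% interval for the annualized rate is below 0.85. Compute that limit with a patient-level robust (sandwich) variance, or from a negative binomial model, with log follow-up time as offset. Keep the exact Poisson interval as a secondary display and report the observed variance/mean ratio.

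In 13.4, say that the 85% and 90% powers are for a comparison with 0.75 under zero overdispersion, and that the 90.5% at 130 patients falls to about 88%, 86%, 83% and 80% at ratios of 1.25, 1.5, 2.0 and 2.5. Add that power against 0.85 at 130 with the Poisson rule stays at about 95% or more over that range, and give the corresponding power for the interval finally chosen.

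The cost is wording and a documented amendment under 17.2; no extra patients or data are needed. The downside is a somewhat wider interval. With full one-year follow-up of 256 patients, power at 0.52 stays at about 99% even at k = 2. With only 130 patient-years it is about 85% there, where the ratio at 0.52 is 1 + 0.52 × 2 = 2.04.
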